## **11. Description of the Study Areas/Regions, Design, Materials and Methods:**

***Study Sites.*** Sites engaged in research include the University of Washington, the University of Michigan, Nyanza Reproductive Health Society (NRHS), and the Nyanza, Rift Valley, and Western Kenya LGBTI Network (NYARWEK). Participant recruitment will occur through the NYARWEK Network. Enrollment, all study visits, and clinical care, including PrEP services provided according to the most recent Kenyan Ministry of Health guidelines, will take place in private rooms at the ***Anza Mapema*** Clinic. Intervention delivery will take place at NYARWEK, at private sites used by NYARWEK organizations, or at a meeting space agreed upon and deemed private and safe by both the participant and a ***Shauriana*** peer facilitator trained to deliver the intervention. In-person research team meetings to monitor the study will also be held in private rooms at the ***Anza Mapema*** Clinic, NYARWEK, or at private sites used by NYARWEK organizations. A description of each site's facilities and other resources are included in “Appendix B: Facilities & Other Resources.”

***Study Population.*** The proposed Aim 1 pilot will include 10 adult HIV-negative GBMSM. The proposed Aim 2 intervention trial will include a population of 60 adult HIV-negative GBMSM, all of whom will be recruited in Kisumu, Kenya. The study team and peer facilitators trained to deliver the intervention will also participate in data collection, by providing feedback on intervention feasibility at routine study team meetings that will be minuted.

***Study Design.*** The Aim 1 work will be a prospective pilot of the intervention and of study procedures other than laboratory testing, in a small group of 10 men over a 3-month period, with visits at baseline, month 1, and month 3. During this pilot test, intervention and clinic visit procedures, including data collection tools, will be revised and improved as needed according to feedback on feasibility, comprehension, burden on participants, and acceptability among pilot participants. The Aim 2 work will be an RCT of the final ***Shauriana*** intervention, to test its acceptability, feasibility, and safety and estimate its initial effect size compared to standard care. The final phase of this study will consist of data analysis and dissemination activities.

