Trial enrollment and randomization. Once consent has been given, participants will be randomized to a study arm. The process of randomization to one of two study arms will be explained carefully and reviewed as part of the informed consent process. Computer-generated randomization will be used to assign participants in a 1:1 ratio to the standard care or intervention group, in blocks of 4, to ensure that equal numbers are randomized across arms. Numbered envelopes indicating the assignment will be prepared in and sealed by the UW CFAR Biometrics Core; study staff will not be aware of an individual's condition until the envelope is opened.

Clinic visits. Consistent with the latest Kenyan guidelines, all trial field-test participants will undergo study procedures at baseline, month 1, month 3, and month 6 at the **Anza Mapema** clinic. As for the pilot study, clinic visits will include HIV counselling and testing, screening for STI symptoms, and individual counselling about HIV prevention methods, including standard of care counselling (information, risk reduction, and PrEP counselling). A standardized physical exam will be performed at each visit, and both blood and urine samples will be collected. For participants taking PrEP, medical history will also focus on PrEP side effects and seroconversion symptoms, and PrEP refills will be provided (monthly for the first 3 months then quarterly). After completing these procedures, RCT participants will complete a detailed ACASI described below. Each of the four clinic visits (baseline, month 1, month 3, and month 6) will take from 1.5 to 2 hours; participants will be reimbursed KSh 500 for each clinic visit.

Standard care. All participants will receive standard care at the *Anza Mapema* Clinic, including standard counseling as described above; screening for depressive symptoms and substance use disorder; monthly *Anza Mapema* peer outreach for education and supply of condoms and lubricants; support group meetings; and social events as described above under “Previous Studies and Rationale.” Attendance at *Anza Mapema* support groups and social events by *Shauriana* study participants will be tracked, as will the content of these group and social events during the study period. To ensure fidelity of delivery for each arm, we will review study progress, procedures, and emergent issues at weekly study meetings.

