Clinical outcomes that will be tracked by the Anza Mapema Clinic using existing data collection instruments include visit attendance, attendance at clinic-sponsored support groups or social events, diagnosis and treatment of STI, HIV test results, PrEP refills, and PrEP-related adverse events and their management. Treatment will be provided for STI syndromes and acute illnesses as needed. All non-scheduled clinic visits will be documented. The study team (both clinic staff and intervention facilitators) will refer participants who need services beyond their capacity to mental health, substance use, advocacy, and/or legal services provided locally. All referrals will be documented.

Men who discontinue PrEP will continue follow-up; PEP will be available for men reporting high-risk exposure while not taking PrEP. Men who seroconvert will be withdrawn from the study and linked to HIV care at *Anza Mapema* or at another HIV clinic of their choice. As described above under “Recruitment,” participants who withdraw before or test positive at the month 1 visit will be replaced; replacement participants in the RCT will undergo randomization and not necessarily be assigned to the arm to which the participant they replace was assigned.

Intervention delivery. Participants assigned to the *Shauriana* intervention will be introduced to an assigned peer facilitator on the day of their enrolment visit, after which telephone, SMS, and/or WhatsApp contacts from peers will begin, with in-person meetings per the intervention schedule described above. For the RCT, the intervention has been expanded to include an initial introductory session where peer facilitators spend time getting to know their assigned participants. Therefore, five core intervention sessions and an optional additional session will be delivered. All peer facilitator contacts with participants and all required and optional intervention sessions will be documented. RCT participants will be reimbursed 350 KSh for their transportation after receiving each of the five core *Shauriana* modules, as participants may need to travel to a safe space for intervention delivery to ensure privacy.

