Exit interviews. At study completion or any visit on which a participant withdraws, an exit interview will be conducted regarding experiences, including any social harms of participation and feedback on standard care or the *Shauriana* intervention. Exit interviews will be conducted by the *Shauriana* Project Research Coordinator, who is based at NYARWEK, using a semi-structured exit interview guide. Notes will be taken and interviews will be recorded using a digital recorder. All participants who complete an exit interview will receive KSh 500 as reimbursement for their time and transport. The topic guide for the exit interviews is included in “[Appendix E: Shauriana Exit Interview Guide](#).”

Schedule of procedures. A table summarizing procedures for the Shauriana study is included in “[Appendix G: Schedule of Procedures](#).”

Power considerations. This project is designed to develop a novel intervention to promote PrEP adherence and sexual health among African GBMSM and to assess its acceptability, feasibility, and safety in a clinical trial setting. It is not designed or powered to determine the overall intervention effect nor the effects of individual components of the intervention. Data on PrEP drug levels and other secondary outcomes in each study arm will help to evaluate whether the intervention is at least as good as standard care and provide some insight into the promise of the intervention to inform larger-scale testing. See Section 13 for statistical analysis plans.

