## **12. Ethical Considerations:**

***Human Subjects Involvement and Characteristics:*** The proposed research is non-exempt human subjects research. Prisoners and children under 18 years of age will not be included. Precautions will be taken as below regarding potential subjects with low literacy. All procedures will be conducted in accordance with 45 CFR Part 46. Protocols will be approved by

the Human Subjects Research Committees (HSRC) at the University of Washington (UW) and by the Maseno University Ethics and Research Committee (MUERC) in Kisumu, Kenya. During both research stages (pilot test and RCT), we will actively solicit feedback from GBMSM participants, as well as from the study team (clinic staff and peer facilitators) regarding the feasibility of the intervention components. In addition, we will hold ongoing discussions with the Anza Mapema Community Advisory Board, within the NYARWEK member network, and with our ethical review boards to ensure the relevance and ethical conduct of the research.

The proposed Aim 1 study will include a population of 10 adult HIV-negative GBMSM recruited in Kisumu, Kenya. The proposed Aim 2 study will include a population of 60 adult HIV-negative GBMSM recruited in Kisumu, Kenya. To be eligible for the *Shauriana* intervention pilot or trial, men must be biologically male at birth and male-identifying, 18 to 35 years of age, resident in the Kisumu area for  $\geq 12$  months, report anal intercourse with a man in the past 3 months, and be willing to provide complete locator information and undergo all study procedures, including HIV testing and counseling (HTC). In addition, men should not be currently participating in any HIV prevention or vaccine study and be planning to remain in the study area for at least 6 months. Men will be excluded if they are unable to understand the study purpose and procedures or unwilling to adhere to study procedures or currently under the influence of alcohol or drugs (assessed by clinic staff during screening) or have a prior diagnosis of HIV infection.

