Trained *Anza Mapema* study staff, fluent in Dholuo, English and Kiswahili, will offer participation to the ongoing study component (i.e., pilot study or RCT participation) using a consent specific to that study component. Each informed consent document will describe the purpose of the specific component of the study described, the procedures to be followed, and the risks and benefits of participation. During the consent process, staff will explain the study procedures, with emphasis on features that differ from routine programmatic services, highlighting the risks and benefits of study participation. Consent documents will be available in Dholuo, English and Kiswahili. If an individual is illiterate, all procedures, risks and benefits will be explained and the individual will be given the option of having a friend or family member or a trained consultant who is not a member of the research staff to be present to further explain the study.

Written informed consent will be obtained from all participants; persons incapable of providing informed consent are excluded. Potential participants who would like to take additional time to consider their enrolment will be encouraged to do so. Participants will be able to opt in or out of optional elements of study participation before signing the consent; these include: iris scanning as biometric identification, text messages as reminders of study visits, digital recording of intervention sessions (pilot test only) and exit interviews (pilot test and RCT). Staff will emphasize that participation is voluntary, and that participants can refuse to answer any question or undergo any procedure or can discontinue participation at any time without penalty. Participants will be informed of the procedures for ensuring confidentiality, including use of unique non-personally identifying ID numbers instead of names on research materials, and the maintenance of data in encrypted computer databases and locked filing cabinets in locked rooms. Enrolled participants will be provided with a signed and dated copy of the informed consent document before they leave the study site.

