## **16. Timeline/Time Frame:**

Aims 1 and 2 of the project (pilot phase and trial of the *Shauriana* intervention) will occur over an 18-month period, from the time all ethical approvals are in place. Piloting will take place in months 1-5 of the proposed work, after training of the peer facilitators and of the *Anza Mapema* Clinic staff on the research protocol. Recruitment for the RCT would take place over months 6-12, with 6-month follow-up for each enrolled participant. As work progresses, we will present abstracts at international and national conferences and submit manuscripts to top-tier journals with an audience inside and outside of Africa.

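### One fixed block size of 4 in a single-clinic trial with visible assignment lets anyone who tracks all earlier assignments know an expected 20 of 60 allocations; varying the blocks removes that certainty but not most of the guessing.

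*Combined protocol and SAP*

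**What the plan says.** Section 11 (Trial enrollment and randomization) describes computer-generated randomization that will "assign participants in a 1:1 ratio to the standard care or intervention group, in blocks of 4, to ensure that equal numbers are randomized". It gives one block size and no stratification factor. Randomization follows consent. Numbered envelopes are prepared and sealed by the UW CFAR Biometrics Core, and study staff are not to know a man's "condition until the envelope is opened". No masking after that moment is described.

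Other places that bear on the point:

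- Section 11 (Study Sites): "Enrollment, all study visits, and clinical care" are all placed at the Anza Mapema Clinic.
- Section 11 (Intervention delivery): men in the intervention arm are "introduced to an assigned peer facilitator on the day of their enrolment visit".
- Section 16: the timeline provides for training of the "Clinic staff on the research protocol", which is the document that prints the block size.
- Section 12 (Human Subjects Involvement and Characteristics): the exclusion for alcohol or drug influence is "assessed by clinic staff during screening".
- Section 12 (Recruitment of Subjects and Consent Procedures): "Potential participants who would like to take additional time to consider their enrolment will be encouraged to do so".
- Section 11 (Power considerations): the study is "not designed or powered to determine the overall intervention effect".

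**The concern.** Sealed envelopes hide what is inside the next envelope. They do not hide what follows from those already opened. In a 1:1 block of 4 used in order, the fourth place is always fixed by the first three, and the third is also fixed whenever the first two match. One clinic, one apparent list, a printed block size and an arm that is visible on the same day are the conditions under which such deduction is easiest.

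Foreknowledge matters only if someone can act on it before consent. The room is limited but not nil. Most criteria are self-reported or factual, but sobriety, ability to understand the study and willingness to follow procedures call for judgement, and a man may defer his decision, so the order of enrolment is not fixed. In addition, section 11 (Recruitment) has NYARWEK peer facilitators in contact with potential participants, and peer facilitators also deliver the intervention.

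If men were steered, these results would be exposed:

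- the comparison of acceptability of study participation between arms, a primary analysis (section 13);
- the comparison of retention between arms (section 13);
- the by-arm estimates of PrEP uptake, adherence, refills and drug levels, which section 13 intends for planning a larger study;
- session attendance and component scores in the intervention arm. These are not arm contrasts, but they would shift if keener men were steered to that arm.

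**Working it through.** **Inputs.** Ratio 1:1, block size 4 (section 11, Trial enrollment and randomization); 60 men, 30 per arm (section 11, Aim 2 Recruitment). A single list is assumed, because no strata are stated.

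**The plan's own figure.** 60 / 4 = 15 complete blocks; 15 x 2 = 30 per arm. The stated 30/30 split is reproduced. The documents give no figure for predictability.

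**Certain allocations, fixed blocks of 4, full view.** There are 6 equally likely orders.

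- In 2 of the 6 (AABB, BBAA) the last two places are determined: 2 certain.
- In the other 4 only the last place is determined: 1 certain.
- Mean per block = (2 x 2 + 4 x 1) / 6 = 4/3.
- Over 15 blocks: 15 x 4/3 = 20 of 60 (33%).
- The total is 15 + Binomial(15, 1/3): minimum 15, maximum 30, and 17 to 24 with probability 0.97.

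**Partial view.** Assume that the observer sees each earlier assignment independently with probability f and knows the block starts. Place 3 is certain with probability f²/3. Place 4 is certain with probability f²: if the first two match (1/3), the observer needs both of them; otherwise (2/3), place 4 is the opposite of place 3, and the observer needs place 3 and the earlier place with the same assignment. The sum is 4f²/3 per block, or 20f² over 60.

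| f (assumed) | Certain of 60 |
|---|---|
| 1 | 20 |
| 0.75 | 11.25 |
| 0.5 | 5 |
| 0.25 | 1.25 |

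**Best guessing, fixed blocks of 4.** The probability of a correct guess is 1/2 at place 1, 2/3 at place 2, 1/3 x 1 + 2/3 x 1/2 = 2/3 at place 3, and 1 at place 4. The sum is 2.833 per block; x 15 = 42.5 of 60, against 30 by chance.

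**Randomly varied blocks of 4, 6 and 8.** Lists of 60 were simulated with the three sizes equally likely. The observer knows the set of sizes and all earlier assignments, but not the current block's size.

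| | Fixed 4 | 4/6/8 |
|---|---|---|
| Certain allocations | 20 | about 1.4 (95% range 0 to 7; none in 59% of lists) |
| Best guesses correct | 42.5 | 40.7 |
| Allocations guessable at 75% odds or better | 20 | about 21 |
| Arms exactly equal at 60 | 100% | about 73% |
| Arms within 2 | 100% | over 99% |
| Largest difference seen | 0 | 4 |

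The excess over chance falls from 42.5 - 30 = 12.5 to 40.7 - 30 = 10.7, about one seventh. An observer who knows no block sizes and always guesses the arm that is behind also scores 40.7 under 4/6/8, so secrecy about the sizes adds almost nothing against guessing.

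**The case against.** The best case for the plan has four parts.

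**Safeguards are in place.** The list is computer-generated, the envelopes are numbered and sealed off site, and consent precedes randomization. Section 12 (Adequacy of Protection from Risks) refers to detailed operating procedures, which are not in the reviewed text and may settle who opens envelopes and in what order. This stands, but none of it stops inference from earlier openings.

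**Twenty is a ceiling.** It needs someone who knows the block size, knows where each block starts and tracks every assignment. This stands. Section 16 provides for staff training on the protocol; it does not show that block size is taught or that a tally is kept. A reader might infer that clinic staff will know a third of the allocations, or that concealment has failed. The documents support neither.

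**The remedy changes little of what drives selection.** A good guess is enough to steer, and best guessing drops by under two of 60. This stands and limits the benefit. A reader might take the fall from 20 to 1.4 as near removal of the problem; the guessing figures show that it is not.

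**The stakes are low.** This is a pilot, and fixed blocks serve its aim of equal numbers. That is a reason to grade the point low. It is not a reason to leave a cheap improvement undone, because the by-arm estimates are meant to be carried into a larger trial.

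**Conclusion.** The point holds as a design choice to consider. Under fixed blocks of 4, a fully informed observer would know an expected 20 of 60 allocations with certainty, and at least 15. This rests on a known block size, a single list used in order and a complete tally; with sight of half of the earlier assignments it is about 5. Replacements are randomized too, so the total may exceed 60, but the expected share stays one third over complete blocks.

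This is an avoidable opportunity for selection, and nothing in the documents shows bias. Varying the blocks takes away nearly all of the certainty and leaves about six sevenths of the guessing advantage. Lack of masking is not a separate fault here, since one arm meets a peer facilitator.

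**What to change.** Before RCT enrolment starts, have the UW CFAR Biometrics Core generate the list with randomly varied blocks of 4, 6 and 8. Replace the block-size wording in section 11 with a statement that permuted blocks of varying size are used, without listing the sizes.

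Costs:

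- a new list from the group that already makes it;
- a full set of newly prepared and sealed numbered envelopes, sent to the clinic in Kisumu;
- one or two protocol sentences and a minor amendment to the two ethics bodies named in section 12, one of which has already approved the protocol;
- a small possible imbalance, at most 4 men in the simulated lists. An exact 30/30 split among men followed is already loosened, because replacements are newly randomized and may go to the other arm.

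No extra participants or staff are needed. The documents do not say whether envelopes already exist or RCT enrolment has begun. If it has, apply the change only to the remaining allocations or leave the list as it is.

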**Table 2. PrEP-oriented and *Shauriana*-Specific Data Elements for Collection by ACASI**

Data Element	Content	Method	Frequency
Primary Outcome Variables			
Acceptability	5-point Likert scales evaluating acceptability of the Shauriana intervention components,  exit interviews for detailed qualitative feedback	ACASI, exit interviews	Quarterly
Feasibility	Visit attendance, session delivery, documentation of peer contacts, minutes of research team meetings	Clinic and intervention data, minutes	Ongoing
Safety	Adverse events reported by participants or study staff; self-reported consequences of study participation in exit interviews	Reports at clinic visits, exit interviews	M1 then quarterly
Secondary Outcome Variables			
PrEP uptake	Two questions on past and ongoing PrEP use	ACASI	Quarterly
PrEP adherence	A series of self-report measures we have used in previous work.	ACASI	Quarterly
PrEP refills	Documented at Anza Mapema for each participant	Clinic data	Quarterly
PrEP drug levels	Urine TFV levels  DBS TFV-DP and FTC-TP levels (if funding permits)	Laboratory	Quarterly
Potential Correlates of Retention and Adherence			
Risk perception	A question on the participant’s self-assessment of his chance of getting HIV/AIDS	ACASI	Quarterly
PrEP knowledge	PrEP knowledge questions (based on relevant literature and completed qualitative research by the team)	ACASI	Quarterly
Motivation/skills	LifeWindows Information-Motivation-Behavioral Skills adherence questionnaire,  adapted for PrEP use based on completed qualitative research by the team.	ACASI	Quarterly
PrEP distrust	PrEP-related distrust, skepticism, trust in providers, and ownership (championing) per [name] et al. 	ACASI	Quarterly
Shared decision making	Participant-reported sharing of decision-making related to PrEP; adapted from Barr et al. 	ACASI	Quarterly
Social support and loneliness	Multidimensional Scale of Perceived Social Support, a 12-item scale of perceived support from family, friends, others 	ACASI	Quarterly
Self-esteem	10-item Rosenberg self-esteem scale,  previously used in this population 	ACASI	Quarterly
Resilience	Coping self-efficacy scale: 13-item version validated in HIV+ GBMSM with depressed mood 	ACASI	Quarterly
Sexual identification	27-item lesbian, gay, and bisexual identity scale (LGBIS),  previously used in Kenya 	ACASI	Quarterly

Laboratory testing. HIV testing at screening and follow-up visits will be performed with two rapid tests (Determine®, Abbott Laboratories, Abbott Park, IL, USA; and First Response®, Premier Medical Corporation, Kachigam, Nani Daman, India), in accordance with the latest Kenyan HIV testing guidelines. Dried blood spots will be collected per an existing SOP at the

Anza Mapema Clinic, and stored for analysis of PrEP drug levels (i.e., detection of TFV-DP and FTC-TP), should funding permit. Safety monitoring in the RCT will be done at a higher standard than is currently available in Kenya, where costs of lab testing have prohibited routine baseline testing and instead use an approach targeted based on signs or symptoms of kidney or liver disease. Serum will be tested at baseline for creatinine level using the Cobas Integra 400 Plus biochemistry analyzer (Roche, Germany), to document normal renal function prior to PrEP start. Baseline serum will also be tested for hepatitis B surface antigen (HBsAg) using SD Bioline HBsAg WB at the CDC-KEMRI laboratory in Kisumu; men who do not have chronic hepatitis B (i.e., those who are HBsAg negative) will be offered hepatitis B vaccination.

Blood and urine aliquots from baseline, month 3, and month 6 will be stored at -80°C in the NRHS laboratory in Kisumu. Urine samples will be shipped on dry ice for testing utilizing the liquid chromatography tandem mass spectrometry (LC-MS/MS) urine tenofovir (TFV) assay developed at Philadelphia FIGHT/Children's Hospital of Philadelphia by [name] and colleagues, currently performed by Molecular Testing Labs in Vancouver, Washington, USA. This assay detects TFV with greater sensitivity than plasma-based measures, with a detection window within 7 days of the last TDF/FTC dose. In addition, dried blood spots will be shipped to Molecular Testing labs for TFV-DP and FTC-TP quantitation using LC-MS/MS to estimate the number of doses taken in the past 7 days. If any participant acquires HIV during the study, HIV-1 genotypic resistance testing will be conducted on stored samples at the CDC-KEMRI laboratory in Kisumu, to determine whether acquired virus is resistant to TDF or FTC.

Exit interviews. At study completion or any visit on which a participant withdraws, an exit interview will be conducted regarding experiences, including any social harms of participation and feedback on standard care or the *Shauriana* intervention. Exit interviews will be conducted by the *Shauriana* Project Research Coordinator, who is based at NYARWEK, using a semi-structured exit interview guide. Notes will be taken and interviews will be recorded using a digital recorder. All participants who complete an exit interview will receive KSh 500 as reimbursement for their time and transport. The topic guide for the exit interviews is included in “[Appendix E: Shauriana Exit Interview Guide](#).”

Schedule of procedures. A table summarizing procedures for the Shauriana study is included in “[Appendix G: Schedule of Procedures](#).”

Power considerations. This project is designed to develop a novel intervention to promote PrEP adherence and sexual health among African GBMSM and to assess its acceptability, feasibility, and safety in a clinical trial setting. It is not designed or powered to determine the overall intervention effect nor the effects of individual components of the intervention. Data on PrEP drug levels and other secondary outcomes in each study arm will help to evaluate whether the intervention is at least as good as standard care and provide some insight into the promise of the intervention to inform larger-scale testing. See Section 13 for statistical analysis plans.

